4.1 Inclusion Criteria

The subject will not be considered eligible for the study without meeting all of the criteria below.

General:

1. Ability to voluntarily provide written, signed, and dated (personally or via a legally authorized representative [LAR]) informed consent or assent as applicable to participate in the study.
2. Subject's parent/LAR demonstrates an understanding, ability, and willingness to fully comply with study procedures and restrictions.
3. Male and female children and adolescents aged 5-17 years, inclusive, at the Baseline Visit (Visit 2).
4. Body weight 18-90 kg at the Screening Visit (Visit 1) and the Baseline Visit (Visit 2).
5. Male, or non-pregnant, non-lactating female who agrees to comply with any applicable contraceptive requirements of the protocol or females of non-childbearing potential.
6. Diagnosed with mild to moderate UC, established by sigmoidoscopy or colonoscopy with compatible histology. Screened subjects may also have an unconfirmed diagnosis of mild to moderate UC; however, the diagnosis of mild to moderate UC must have been established by sigmoidoscopy or colonoscopy with compatible histology prior to the Baseline Visit (Visit 2).

7. Subject is able to swallow the investigational product whole.

Double-blind Acute Phase:

8. Partial UC-DAI score ≥ 2 (with a combined rectal bleeding **and** stool frequency score ≥ 1 **and** PGA=1 or 2) **and** with mucosal appearance (endoscopy score)=2 or 3 at the Baseline Visit (Visit 2), for which 5-ASA would be used as part of normal treatment.
9. If the subject is on 5-ASA treatment prior to study entry, then the dose must be stable. Stable therapy is defined as no change in dose, or no initiation of 5-ASA, from the onset of the current acute flare through discontinuation of therapy (required at the Baseline Visit; Visit 2). See exclusion criterion 28 for an additional 5-ASA dose-related requirement.

Double-blind Maintenance Phase:

10. Partial UC-DAI ≤ 1 (with rectal bleeding=0 **and** stool frequency ≤ 1 **and** PGA=0) **and** with mucosal appearance (endoscopy score)=0 or 1 at the Baseline Visit (Visit 2).

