Subjects may enter the Double-blind Maintenance Phase directly following the Baseline Visit (Visit 2) if they have a partial UC-DAI ≤ 1 (with rectal bleeding=0 and stool frequency ≤ 1 and PGA=0) and with mucosal appearance (endoscopy score) = 0 or 1 at that visit.

MMX mesalamine/mesalazine is dosed once daily by mouth. The selection of doses in this study is based on an approximate average of 43mg/kg for the low dose and 85mg/kg for the high dose in the 3 lower weight groups (18 to ≤ 23 kg, > 23 to ≤ 35 kg and > 35 to ≤ 50 kg). These doses were selected based on standard of care dosing for other 5-ASA products in the pediatric population and pharmacokinetic dosing results. The dosing for the highest weight group (> 50 to ≤ 90 kg) is based on adult UC experience.

[figure not shown]
Minimum enrollment criteria have been agreed with FDA as follows, based on subject weight group:

Table 1: Minimally Required Number of Subjects per Weight Group

Weight Group	Low Dose (mg/day)	High Dose (mg/day)	Number of Subjects in Combined Low and High Dose ^a
18 to <23kg	900	1800	2
>23 to ≤35kg	1200	2400	12
>35 to ≤50kg	1800	3600	18
>50 to ≤90kg	2400	4800	36

^a Randomization will be stratified by weight group with the aim of creating balance between the 2 dose groups within a weight group

Figure 1: Study Design Flow Chart

PGA=Physician's Global Assessment; UC-DAI=Ulcerative Colitis Disease Activity Index.

^a Subjects with partial UC-DAI ≥ 2 (with a combined rectal bleeding and stool frequency score ≥ 1 and PGA=1 or 2) and with mucosal appearance (endoscopy score)=2 or 3.

^b Subjects with partial UC-DAI ≤ 1 (with rectal bleeding=0 and stool frequency ≤ 1 and PGA=0) and with mucosal appearance (endoscopy score)=0 or 1.

Notes: Solid boxes indicate study phases. Dashed ellipses indicate decision points.

Subjects will initially be randomized into either the 8-week Double-blind Acute Phase or the 26-week Double-blind Maintenance Phase based on partial UC-DAI and mucosal appearance scores. Subjects who do not achieve a clinical response or who have withdrawn from the Double-blind Acute Phase after a minimum of 2 weeks and, in the investigator's opinion, have not benefited from treatment in the Double-blind Acute Phase may enter the Open-label Phase. Subjects without a clinical response after completion of acute treatment in the Open-label Acute Phase must be withdrawn.

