4.3.4 Pediatric Ulcerative Colitis Activity Index

The PUCAI is a physician-administered measure that focuses on 6 key signs and symptoms of UC and activity limitations ([Turner et al., 2007](#)). The PUCAI yields a total score ranging from 0-85 with higher scores being worse. Recommended cut-off scores to differentiate disease activity are <10 (remission); 11-30 (mild); 31-64 (moderate) and >65 (severe) ([Turner et al., 2009](#)). Evaluation of the construct validity of the PUCAI revealed that it was highly correlated with physician's global assessment of disease activity and PUCAI scores were highly predictive of the need for escalating medical therapy ([Turner et al., 2009](#)).

Only sites who have executed a sub-license with Shire for PUCAI use will be able to collect PUCAI data for the study.

Item	Points
1. Abdominal pain	
No pain	0
Pain can be ignored	5
Pain cannot be ignored	10
2. Rectal bleeding	
None	0
Small amount only, in less than 50% of stools	10
Small amount with most stools	20
Large amount (>50% of the stool content)	30
3. Stool consistency of most stools	
Formed	0
Partially formed	5
Completely unformed	10
4. Number of stools per 24 hours	
0–2	0
3–5	5
6–8	10
>8	15
5. Nocturnal stools (any episode causing wakening)	
No	0
Yes	10
6. Activity level	
No limitation of activity	0
Occasional limitation of activity	5
Severe restricted activity	10
Sum of PUCAI (0–85)	

© Copyright to The Hospital for Sick Children,
Toronto, Canada, 2006.

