5.8.2.1 Double-blind Acute Phase

- The proportion of subjects with a clinical and endoscopic response at Week 8, defined as UC-DAI ≤ 2 with rectal bleeding=0 and stool frequency ≤ 1 and PGA=0, and with mucosal healing (endoscopy score ≤ 1) based on central reading. In addition, there must be at least a 1-point reduction in endoscopy score from baseline. This endpoint will be compared between treatment arms using a continuity corrected chi-squared test. If any of the expected cell counts are very low (i.e., less than 5), then Fisher's Exact Test will be used as an alternative analysis method. Subjects with missing data at Week 8 will be assumed not to have had a clinical response. Subjects who completed week 8 but who did not have central reading endoscopies at both baseline and week 8 will be excluded.
- The proportion of subjects with a clinical and endoscopic response at Week 8, defined as UC-DAI ≤ 2 with rectal bleeding=0 and stool frequency ≤ 1 and PGA=0, and with mucosal healing (endoscopy score ≤ 1) based on local reading. In addition, there must be at least a 1-point reduction in endoscopy score from baseline. This endpoint will be compared between treatment arms using a continuity corrected chi-squared test. If any of the expected cell counts are very low (i.e., less than 5), then Fisher's Exact Test will be used as an alternative analysis method. Subjects with missing data at Week 8 will be assumed to be treatment failures. Subjects with missing data at Week 8 will be assumed not to have had a clinical response. Subjects who completed week 8 but who did not have local reading endoscopies at both baseline and week 8 will be excluded.
- The change in the DUCS score from baseline to Week 8 of the Double-blind Acute Phase. This endpoint will be compared between treatment arms using an analysis of covariance (ANCOVA), including treatment arm as a factor and the baseline DUCS score as a covariate in the model.
- The percentage of subjects with an improvement (change of ≥ 20 points) in PUCAI score from baseline to Week 8 of the Double-blind Acute Phase. This endpoint will be compared between treatment arms using a continuity corrected chi-squared test. If any of the expected cell counts are very low (i.e., less than 5), then Fisher's Exact Test will be used as an alternative analysis method. Subjects with missing data at Week 8 will be assumed not to have had a clinical response.

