5.8.3.2 PUCAI

- The PUCAI will be summarized by visit and treatment arm (as applicable) for each study phase. These tables will include both continuous and categorical [<10 (remission); 10-34 (mild); 35-64 (moderate) and 65 or above (severe)] summaries.
- The components of the PUCAI score (abdominal pain, rectal bleeding, stool consistency, number of stools in 24 hours, nocturnal stools, and activity level) will be summarized individually by visit and treatment arm (as applicable) for each study phase.

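### The acute PUCAI improvement endpoint needs a 20-point change, but acute entry has no PUCAI floor, so a child who starts below 20 cannot be counted as improved even at a score of 0

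*SAP*

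**What the plan says.** **Endpoint.** SAP 5.8.2.1 lists "The percentage of subjects with an improvement (change of ≥ 20 points) in PUCAI score from baseline to Week 8" as an acute-phase secondary endpoint, and Protocol 9.8.3.1 sets the same threshold. The arms are compared with a continuity-corrected chi-squared test, or Fisher's exact test if expected counts are low. A missing Week 8 result counts as non-response. SAP 5.8.2 assigns the phase's Safety Analysis Set, with no restriction on baseline PUCAI.

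**Entry.** Protocol 4.1 takes children "Diagnosed with mild to moderate UC, established by sigmoidoscopy or colonoscopy with compatible histology". The activity rule for the acute phase, in SAP 3.1 (Figure 1, footnote a), is "Subjects with partial UC-DAI ≥ 2 (with a combined rectal bleeding and stool frequency score ≥ 1 and PGA=1 or 2", together with an endoscopy score of 2 or 3. No inclusion or exclusion criterion in Protocol 4.1 or 4.2 mentions PUCAI.

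**Scale.** SAP 4.3.4 says "The PUCAI yields a total score ranging from 0-85 with higher scores being worse" and prints the six-item scoring table. SAP 5.8.3.2 plans "categorical [<10 (remission); 10-34 (mild); 35-64 (moderate) and 65 or above (severe)] summaries" by visit and arm in each phase; for the acute phase this is Table 14.2.2.2.6. Reaching a score below 10 is an endpoint only in maintenance (SAP 5.8.2.2).

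**Availability.** Only sites that have executed a sublicense can collect PUCAI (SAP 4.3.4; Protocol 7.2.4.1).

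**The concern.** A responder definition based on a fixed fall works only if every analysed subject can fall that far. This phase recruits mild disease on a different index, and the SAP's mild PUCAI category begins at 10. Some eligible children may therefore be non-responders before they take a dose. The same child could be a responder on the primary endpoint and a non-improver on PUCAI.

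The SAP describes an estimation study with descriptive p-values, so the reported percentages are the product. A built-in ceiling makes the PUCAI percentage hard to interpret, because a low figure could reflect poor response or low starting scores. Children who cannot meet the definition on either dose also contribute nothing to the comparison between doses.

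**Working it through.** **1. Reproduce the stated scale.** The item maxima in SAP 4.3.4 are pain 10, bleeding 30, consistency 10, stool number 15, nocturnal stools 10 and activity 10. Their sum is 10 + 30 + 10 + 15 + 10 + 10 = 85, which agrees with the stated range of 0 to 85. Enumerating all 3 × 4 × 3 × 4 × 2 × 3 = 864 item patterns gives every multiple of 5 from 0 to 85 and no other total.

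**2. Can an eligible child start below 20?** Take a child with streaks of blood (UC-DAI bleeding 1), stool frequency 0, PGA 1 and endoscopy 2.

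- Partial UC-DAI = 1 + 0 + 1 = 2, and combined bleeding and stool score = 1. The acute activity criteria are met.
- On PUCAI, a small amount of blood in fewer than half of stools scores 10. With every other item at 0 the total is 10. If the child passes 3 to 5 stools a day, the total is 10 + 5 = 15.

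This is not a single odd case. Twenty item patterns that include some bleeding or a non-zero stool-number score total 10 or 15. A score of 15 is mild under both bands in the SAP. A score of 10 is mild under SAP 5.8.3.2 but falls between the categories in SAP 4.3.4.

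**3. What can each baseline achieve?** The largest possible fall equals the baseline score.

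| Baseline | Largest fall | Week 8 scores counted as improved | Remission scores (0 or 5) not counted |
|---|---|---|---|
| 10 | 10 | none | 0, 5 |
| 15 | 15 | none | 0, 5 |
| 20 | 20 | 0 | 5 |
| 25 | 25 | 0, 5 | none |
| 30 | 30 | 0, 5, 10 | none |

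From 25 upward every child who reaches remission is counted. The mismatch affects only baselines of 20 or less.

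**4. Effect on the rate and the contrast.** Let f be the share of analysed children starting below 20, equal in the two arms. The highest attainable rate is 1 − f. If d is the arm difference among children starting at 20 or more, the difference in the whole set is (1 − f) × d. The documents give neither f nor d. The values below are assumptions, with rates of 45% and 65% among those starting at 20 or more, so d = 20 points.

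| Assumed f | Highest attainable rate | Difference in whole set (points) |
|---|---|---|
| 0% | 100% | 20 |
| 10% | 90% | 18 |
| 20% | 80% | 16 |
| 30% | 70% | 14 |
| 40% | 60% | 12 |

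The table shows the mechanism; it is not a forecast. It also takes every analysed child to have a PUCAI score.

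**5. What a remission route would change.** Counting a decrease of at least 20 points or a Week 8 score below 10, among baselines of 10 or more, reclassifies five transitions: 10 to 0, 10 to 5, 15 to 0, 15 to 5 and 20 to 5. Nothing changes from baseline 25 upward.

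**The case against.** Much of the opposing case stands.

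- **Remission is not hidden.** SAP 5.8.3.2 and Table 14.2.2.2.6 give the share below 10 at Week 8 by arm, and listing 16.2.6.5 gives individual scores. A reader might infer that recovery in mild children goes unreported; the documents do not support that. However, those summaries are not linked to baseline or to the improvement endpoint. Shift tables are specified for UC-DAI components (SAP 5.8.3.1), and the table list has none for PUCAI.
- **No direction of bias.** The floor applies equally to both arms, and randomisation should balance low baselines on average. A reader might infer that it favours one dose; nothing shows this.
- **The endpoint is estimated correctly as defined.** A fixed minimum change is a legitimate definition of improvement. Calling the rate understated presupposes a different endpoint.
- **Counts cannot be given.** It is tempting to apply a percentage to the 53 acute subjects, but PUCAI exists only at licensed sites and their share is not stated. If children at other sites count as non-responders under the missing-data rule, missing PUCAI could lower the ceiling more than the baseline floor does. For example, with PUCAI available in 60% (assumption) and f of 10% to 30%, the ceiling is 0.60 × 0.90 = 54% down to 0.60 × 0.70 = 42%.
- **A replacement endpoint has faults of its own.** Adding remission would count 10 to 5, a single 5-point step, alongside a 20-point fall.

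None of this answers the central fact: some eligible children cannot meet the definition, and no planned analysis separates them.

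**Conclusion.** The point holds as a limited defect of definition. Under the plan's own entry rule and scoring table, an eligible child with baseline PUCAI below 20 cannot be counted as improved, and a child going from 20 to 5 is not counted despite reaching remission. This caps the attainable rate in both arms and can shrink the observed difference between doses. The logic rests only on the documents. The size does not: it depends on the share starting below 20 and on PUCAI availability, and neither is stated.

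A reader might go further and conclude that the prespecified endpoint should be replaced. The documents do not require that. This is one secondary endpoint in an unpowered estimation study, the threshold is legitimate for children who can reach it, and acute remission is already tabulated. A supportive addition is the proportionate response.

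**What to change.** Keep the prespecified endpoint and its analysis set. In SAP 5.8.2.1, before unblinding:

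1. State the threshold as a decrease of at least 20 points, so that the direction is explicit.
2. Add two supportive analyses by arm:
   - (a) a decrease of at least 20 points, among subjects with baseline PUCAI of 20 or more;
   - (b) a decrease of at least 20 points, or PUCAI below 10 at Week 8, among subjects with baseline PUCAI of 10 or more.
3. Report the number of subjects per arm with baseline PUCAI below 20, so that readers can see how far the ceiling matters.

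Both restrictions use a baseline value, so the comparison remains between randomised groups. The data are already collected at licensed sites. The cost is SAP wording, the derivations and some extra table rows. Analysis (a) has a smaller denominator, and (b) mixes response with remission, so both should be labelled supportive only.

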5.8.2.2 Double-blind Maintenance Phase

- The proportion of subjects who have maintained a clinical and endoscopic response at Week 26, defined as UC-DAI ≤ 2 with rectal bleeding=0 and stool frequency ≤ 1 and PGA=0 and with mucosal healing (endoscopy score ≤ 1) based on central reading. This endpoint will be compared between treatment arms using a CMH test stratifying by Week 8 responder status. Subjects with missing data at Week 26 will be assumed not to have had a clinical response. If there are an insufficient number of subjects with central reading endoscopy data, then the CMH test will not be performed. The number and percentage of subjects with clinical and endoscopic response – based on central response will be presented by treatment arm.
- The proportion of subjects who have maintained a clinical and endoscopic response at Week 26, defined as UC-DAI ≤ 2 with rectal bleeding=0 and stool frequency ≤ 1 and PGA=0, and with mucosal healing (endoscopy score ≤ 1) based on local reading. This endpoint will be compared between treatment arms using a CMH test stratifying by Week 8 responder status. Subjects with missing data at Week 26 will be assumed not to have had a clinical response. If there are an insufficient number of subjects with central reading endoscopy data, then the CMH test will not be performed. The number and percentage of subjects with clinical and endoscopic response – based on local response will be presented by treatment arm.
- The change in the DUCS score from Double-blind Maintenance Phase Week 0 to Week 26. This endpoint will be compared between treatment arms using an analysis of covariance, including treatment arm as a factor, the DUCS score at Double-blind Maintenance Phase Week 0 and Week 8 responder status as covariates in the model.
- The percentage of subjects in remission (PUCAI < 10) at Double-blind Maintenance Phase Week 26. This endpoint will be compared between treatment arms using a CMH test stratifying by Week 8 responder status. Subjects with missing data at Week 26 will be assumed not to have had a clinical response.

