2.2.3 Exploratory Objectives

3. STUDY DESIGN

3.1 Study Design and Flow Chart

This study will enroll male and female children and adolescents aged 5-17 years. This is a prospective, parallel-group study with a Screening Period of 3 to 21 days, an 8-week Double-blind Acute Phase, and a 26-week Double-blind Maintenance Phase. More than 100 subjects will be screened, and up to 80 subjects will be enrolled in the Double-blind Acute Phase of the study. More than 65 subjects will be screened (in addition to an expected 28 subjects who will enter the Double-blind Maintenance Phase from one of the Acute Phases) and at least 80 subjects will be enrolled in the Double-blind Maintenance Phase of the study.

Subjects who do not meet the all the eligibility criteria for either the Double-blind Acute Phase or the Double-blind Maintenance Phase will be considered screen failures. Subjects may be rescreened after consultation with the medical monitor.

A minimum of 1 score each for stool frequency and rectal bleeding must be available in order to randomize subjects into either the Double-blind Acute Phase or the Double-blind Maintenance Phase (see Section 7.2.1.1 for details). Subjects with no symptom score data available will be considered screen failures as these symptom score data are used to calculate the partial UC-DAI score needed for enrollment.

Each of these phases includes 2 treatment arms, and subjects will be randomized at the beginning of each phase to 1 of 2 doses (low and high dose) of MMX mesalamine/mesalazine (900-4800mg/day, given once daily), stratified by weight group. There is an additional 8-week, Open-label Acute Phase for subjects who do not achieve a clinical response or who have withdrawn from the Double-blind Acute Phase and have met certain criteria (see Section 7.1.3). Clinical response is defined as partial UC-DAI ≤ 1 (with rectal bleeding=0 **and** stool frequency ≤ 1 **and** Physician's Global Assessment [PGA]=0) at the end of the Double-blind Acute Phase.

In this Open-label Acute Phase, subjects are treated with the high dose of MMX mesalamine/mesalazine for their weight group.

Subjects with a clinical response after completion of treatment in either the Double-blind Acute Phase or the Open-label Acute Phase will be eligible to enter the Double-blind Maintenance Phase based on partial UC-DAI score (ie, without additional endoscopy).

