4.3 Re-randomization

Subjects with a clinical response, ie, partial UC-DAI \leq 1 (with rectal bleeding=0 *and* stool frequency \leq 1 *and* PGA=0) after completion of treatment in either the Double-blind or the Open-label Acute Phases will be eligible for re-randomization into the Double-blind Maintenance Phase provided they still meet all Baseline Visit (Visit 2) inclusion and exclusion criteria (where re-assessed).

Note that an additional eligibility endoscopy is not required for entry into the Double-blind Maintenance Phase for subjects who achieve a clinical response after completion of treatment in either the Double-blind Acute Phase or the Open-label Acute Phase.

Subjects eligible for either the Double-blind Acute or the Double-blind Maintenance Phase can be re-randomized if they initially failed randomization for the following reasons: incorrect use of IVRS, late or missing central laboratory or endoscopy results, or other reasons of this type as long as they meet inclusion and exclusion criteria. Re-randomization can only take place after consultation with the medical monitor.

Subjects may be re-randomized into the Double-blind Maintenance Phase if they turned 18 years of age during participation in either Acute Phase of the study.

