During this study, an attempt will be made to collect endoscopy data in approximately 30% of subjects at the end of the Acute Phase (combined Double-blind and Open-label) and approximately 30% at the end of the Double-blind Maintenance Phase. In addition, data from endoscopies performed as a part of routine clinical care during a subject's participation in the study will be collected.

Endoscopies will be centrally read and scored for this study, and endoscopic video or photographs must be provided to the central reader for each endoscopy performed. Video images are preferred; however, photographic images will be accepted when video images are not of sufficient quality, as determined by the central reader during individual site image evaluation prior to enrollment at the site. Further details of requirements for video and photographic images will be provided to study sites under separate cover by the central reader. All endoscopies should be performed by the same investigator/endoscopist, if possible, to ensure consistency in endoscopy.

Please see [Appendix 2](#) for the modified full UC-DAI.

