3. STUDY DESIGN

3.1 General Description

This study will be conducted in children and adolescents (aged 5-17 years) to collect data on the safety and efficacy of MMX mesalamine/mesalazine in this population. This study is a PREA post-approval commitment with the US FDA and is intended to provide estimates of clinical response for 2 doses (low and high) across a range of weight groups.

This study will enroll male and female children and adolescents aged 5-17 years. This is a prospective, parallel-group study with an 8-week Double-blind Acute Phase, and a 26-week Double-blind Maintenance Phase. More than 100 subjects will be screened, and up to 80 subjects will be enrolled in the Double-blind Acute Phase of the study. After agreement with FDA, the sample size for the Double-blind Acute Phase has been reduced to 53 subjects due to difficulties with recruitment.

More than 65 subjects will be screened (in addition to an expected 28 subjects who will enter the Double-blind Maintenance Phase from one of the Acute Phases) and at least 80 subjects will be enrolled in the Double-blind Maintenance Phase of the study.

Each phase includes 2 treatment arms, and subjects will be randomized at the beginning of each phase to 1 of 2 doses (low and high dose) of MMX mesalamine/mesalazine (900-4800mg/day, given once daily), stratified by weight group. There is an additional 8-week, Open-label Acute Phase for subjects who do not achieve a clinical response or who have withdrawn from the Double-blind Acute Phase and have met certain criteria (see [Figure 1](#)). Clinical response is defined as partial Ulcerative Colitis Disease Activity Index (UC-DAI) ≤ 1 (with rectal bleeding=0 and stool frequency ≤ 1 and Physician's Global Assessment [PGA] =0) at the end of the Double-blind Acute Phase. In this Open-label Acute Phase, subjects are treated with the high dose of MMX mesalamine/mesalazine for their weight group.

Subjects with a clinical response after completion of treatment in either the Double-blind Acute Phase or the Open-label Acute Phase will be eligible to enter the Double-blind Maintenance Phase based on partial UC-DAI score (i.e., without additional endoscopy).

Subjects without a clinical response after completion of acute treatment in the Open-label Acute Phase must be withdrawn.

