5.2.7 Double-blind Maintenance Phase Safety Analysis Set

The Double-blind Maintenance Phase Safety Analysis Set will consist of randomized subjects who have taken at least 1 dose of investigational product during the Double-blind Maintenance Phase.

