7.6.2 Prior Response Status

The primary and secondary efficacy endpoints will be summarized for the Double-blind Maintenance Phase by prior response status (entered Maintenance Phase directly, responder at Week 8 in Double-blind Acute Phase, responder at Week 8 in Open-label Acute Phase). This analysis will provide information on the durability of response with respect to the prior treatment with either MMX or other 5-ASA treatment.

In addition, the primary and secondary efficacy endpoints will be summarized for the Double-blind Maintenance Phase by prior response status (entered Maintenance Phase directly, responder at Week 8 in Double-blind Acute Phase, responder at Week 8 in Open-label Acute Phase) and prior treatment (low-dose MMX, high-dose MMX, and 5-ASA by medication preferred term). This analysis will provide information on the durability of response with respect to the prior MMX dose group or other 5-ASA treatments by preferred term.

The number (n, %) of subjects with a clinical response at Week 26 and difference between treatment arms for each stratum, together with the 95% CI (2-sided), and associated p-value will be presented.

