8.2 Derived Efficacy Endpoints

- Stool frequency and rectal bleeding score:
 - For both stool frequency and rectal bleeding, the symptom score (collected via the electronic diary [e-diary]) is defined as the average of the scores from the last available 3 days from the 5 days immediately prior to the visit (days -1 to -5). If there are fewer than 3 days of data available during days -1 to -5, the average will be calculated from any available days within the period. If there are no available days during the period, then the symptom score will be missing for that visit. Data collected on days when bowel preparations have been administered or when endoscopy has been performed will be excluded.
 - For stool frequency and rectal bleeding, the symptom score will be grouped into a category (0, >0 - <1, 1 - <2, 2 - <3, and 3).
- Partial UC-DAI score:
 - Sum of rectal bleeding score, stool frequency score and PGA score
- Full UC-DAI score:
 - Sum of rectal bleeding score, stool frequency score, PGA score and endoscopy score
- Clinical response: partial UC-DAI ≤ 1 (rectal bleeding=0 and stool frequency ≤ 1 and PGA=0)
- Clinical and endoscopic response: UC-DAI ≤ 2 with rectal bleeding=0 and stool frequency ≤ 1 and PGA=0, and mucosal healing (endoscopy score ≤ 1) based on central reading
- Week 8 responder status is defined based on clinical response: entered Maintenance Phase directly, responder at Week 8 of the Double-blind Acute Phase, or responder at Week 8 of the Open-label Acute Phase.

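### The Week 26 endpoint titled maintained clinical and endoscopic response sets no Week 0 endoscopic condition, so each dose's rate mixes maintained healing with new healing and persistent inflammation

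*SAP*

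**What the plan says.** **Endpoint.** SAP 5.8.2.2 defines "The proportion of subjects who have maintained a clinical and endoscopic response at Week 26" by Week 26 status: UC-DAI 2 or less, no rectal bleeding, stool frequency 1 or less, PGA 0 and endoscopy score 1 or less. There is a central-reading and a local-reading version. Protocol 9.8.3.2 agrees. The derivation in SAP 8.2 ends "and mucosal healing (endoscopy score ≤ 1) based on central reading" and refers to no earlier visit.

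**Analysis set.** SAP 5.2.7 takes "randomized subjects who have taken at least 1 dose of investigational product during the Double-blind Maintenance Phase", with no Week 0 endoscopy requirement.

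**Entry.** Direct entrants need an endoscopy score of 0 or 1 (protocol 4.1, criterion 10), judged on the local reading if the central one is unavailable (protocol 4.2, criterion 30; 7.1.1.1). For acute-phase responders, protocol 4.3 says: "Note that an additional eligibility endoscopy is not required for entry into the Double-blind Maintenance Phase". Protocol 3.1 and SAP 3.1 agree. Protocol 7.1.2.3 and 7.1.3.3 let a subject who was not scoped at Visit 3.2 or 4.2 stay in the study. The last endoscopy such a child must have had is the one at acute entry, where the score had to be 2 or 3 (protocol 4.1, criterion 8).

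**Contrary text.** Footnote d of protocol Table 1 and SAP Table 5 makes an endoscopy score of 0 or 1 a condition for moving from the Double-blind Acute Phase into Maintenance. Footnote b of protocol Table 2 and SAP Table 6, for the Open-label Acute Phase, has no such condition.

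**Coverage.** Protocol 7.2.1.2 says that "an attempt will be made to collect endoscopy data in approximately 30% of subjects at the end of the Acute Phase" (both acute phases combined), with a similar target at the end of Maintenance.

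**Related outputs.** SAP 7.6.2: "The primary and secondary efficacy endpoints will be summarized for the Double-blind Maintenance Phase by prior response status". SAP 5.8.3.1 plans shift tables of UC-DAI components, including endoscopy, from Week 0 to Week 26.

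**The concern.** To maintain a state, a subject must have been in it at the start. That holds for the primary Maintenance endpoint, because every entrant meets the clinical response definition at Week 0. It does not hold for the endoscopic version. Two records that the body text allows show this:

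- Acute-entry endoscopy 3, not scoped at the end of acute treatment, Week 26 clinical criteria met with endoscopy 1. Counted as maintained, although healing is first shown at Week 26.
- Clinical response at the end of acute treatment with endoscopy 2, Week 26 clinical criteria met with endoscopy 2. Counted as not maintained, although there was no endoscopic response to lose.

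SAP 5.1 presents the trial as one that estimates response for each of two doses, so the meaning of each dose's rate is the main product. SAP 5.8.2.2 also drops the CMH test if too few central readings exist, leaving pooled counts and percentages by arm as the main result. The acute-phase counterpart in SAP 5.8.2.1 does use paired logic: it requires a 1-point endoscopic reduction and excludes Week 8 completers without endoscopies at both visits. The Maintenance bullets have no equivalent.

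**Working it through.** The documents give no expected rate or precision for this endpoint, so there is no figure to reproduce. The check sizes the affected group.

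**Inputs.** Expected roll-overs 28 and Maintenance N at least 80 (protocol 9.6, SAP 3.5). Acute N up to 80 (protocol 9.6), reduced to 53 (SAP 3.5). End-of-acute endoscopy coverage about 30% (protocol 7.2.1.2).

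**Subjects with no Week 0 endoscopy** = roll-overs × (1 − coverage).

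- Roll-over share: 28/80 = 35%, leaving 52 direct entrants.
- 28 roll-overs, 30% coverage: 28 × 0.70 = 19.6, or 24.5% of 80. Range: 28 (35%) at 0% coverage to 11.2 (14%) at 60%.
- Roll-overs assumed to scale with acute N: 28 × 53/80 = 18.6. At 30% coverage, 18.6 × 0.70 = 13.0, or 16% of 80. Range: 18.6 (23%) at 0% to 7.4 (9%) at 60%.
- Most favourable case on that scaling: 0.30 × 53 = 15.9 scopes, all in roll-overs, leaves 18.6 − 15.9 = 2.7, about 3 (3% of 80).

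These counts leave out roll-overs who were scoped and scored 2 or 3. The body text does not make the result an entry condition, so being scoped does not show healing.

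**Illustration with assumed rates.** Suppose 70% of the other 60.4 subjects (80 − 19.6, taking every scoped roll-over as healed) and 30% of the 19.6 unscoped subjects meet the Week 26 rule. The pooled rate is 0.755 × 0.70 + 0.245 × 0.30 = 0.602. That is about 10 points below 70%, from population mix alone.

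**Size of a row restricted to documented Week 0 healing** = 52 + 28 × 0.30 × q, where q is the assumed share healed among scoped roll-overs. This gives 54.5 at q = 0.3, 56.2 at q = 0.5 and 60.4 at q = 1. With 18.6 roll-overs and total N held at 80, the same sum gives 63.1 to 67.0.

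**Precision.** The worst-case 95% half-width for the arm difference is 1.96 × √(4 × 0.25/N), at p = 0.5 with 1:1 allocation: 21.9 points at N = 80, 25.3 at N = 60, 27.2 at N = 52 (direct entrants only).

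**The case against.** **The wording is the fault, not the measure.** The secondary objective (SAP 2.2.2) is to assess clinical and endoscopic response. Protocol 7.2.1 and the titles of Tables 14.2.2.1.5 and 14.2.2.1.9 speak of response at Week 26, without *maintained*. This stands: Week 26 status is a legitimate quantity and answers that objective. It is not what the endpoint in SAP 5.8.2.2 and protocol 9.8.3.2 claims to be.

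**The dose comparison.** A reader might infer that the contrast between doses is biased. The documents do not support that. Subjects are randomized, or re-randomized, at Maintenance Week 0, and the CMH test is stratified by entry route. Mixed mucosal status at Week 0 affects interpretation, not the fairness of the comparison.

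**Existing outputs.** Tables 14.2.2.1.6 and 14.2.2.1.10 give the composite by entry route, and the direct-entry row comes close to the intended population. Table 14.2.2.2.19 shows endoscopy shifts for both readings. These help, but each roll-over row still mixes healed, unhealed and unscoped children. The shift table covers the endoscopy component rather than the composite, and can say nothing about a child with no Week 0 scope.

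**Footnote d.** If it governs, neither example record could enter from the Double-blind Acute Phase, and the problem shrinks to Open-label roll-overs. It conflicts with the body text, so it cannot be counted as a safeguard until the passages are reconciled.

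**Fewer misclassified subjects than the counts suggest.** Visit 3.2 endoscopy is directed at subjects not entering the Open-label Phase, so roll-overs may be scoped more often than 30%. Being wrongly counted as maintained also needs a Week 26 scope: at an even 30%, about 6 of the 20 (19.6 × 0.30 = 5.9). Both are fair. But the SAP does not say whether an absent Week 26 endoscopy is missing data; if it is, the other 14 or so count as not having maintained a state never shown.

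**Conclusion.** The point holds as one about the meaning of a secondary endpoint. The Week 26 rule sets no Week 0 endoscopic condition, and under the body text an expected 35% of the Maintenance Phase may enter without documented healing. About 20 of 80 have no Week 0 endoscopy on the stated 28 roll-overs with 30% coverage applied evenly. The figure is about 13 if roll-overs scale with the acute sample, and about 3 if in addition every expected scope falls in a roll-over. Scaling and even coverage are assumptions; the documents state neither. Scoped but unhealed roll-overs add to each figure.

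A reader might subtract 16 scopes from 28 and take 12 (15%) as the floor, since SAP 3.5 still shows 28 beside the reduced sample of 53. That mixes bases: the protocol gives 28 beside up to 80 acute subjects, while the 16 comes from 53, and the SAP does not say that 28 was re-derived.

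The primary endpoint is unaffected, and no power claim is at stake.

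**What to change.** In SAP 5.8.2.2, with a matching entry in SAP Section 6:

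- Keep the all-subject result and title it *clinical and endoscopic response at Week 26*.
- Report *maintained clinical and endoscopic response* only for subjects with a documented Week 0 endoscopy score of 1 or less on the same reading: central for the central version, local for the local version. Do not assume this for all direct entrants, because entry may have rested on a local reading.
- Show the remaining subjects in two separate rows: Week 0 score 2 or more, and Week 0 endoscopy not done or not read.

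Footnote d of protocol Table 1 and SAP Table 5 must be reconciled with protocol 3.1, 4.3 and 7.1.2.3 and SAP 3.1.

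The cost is SAP wording and one further split of planned tables, with no new data. The *maintained* row falls to about 54 to 60 of 80 on the 28 roll-over figure, and lower in the central version if some direct entrants have only a local reading. The worst-case half-width for the arm difference rises from about 22 to 25–27 points. The all-subject result keeps its full denominator.
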